5 STUDY DESIGN

- This is a Prospective, Vehicle Controlled, Double-Blind, Multicenter, Randomized Phase II Trial, comparing the effect of twice daily B244 applications for 4 weeks vs vehicle applications on treatment of mild to moderate pruritus associated with atopic dermatitis.
- Approximately 576 subjects may be enrolled.
- The total duration of the study will be approximately 11 weeks. Participants will report for a Screening visit and if all inclusion/exclusion criteria are met, subjects will go through a two-week washout phase (see Section 10.6.2) before reporting for a Baseline visit.
- After screening and baseline, participants will be randomized to one of two doses of B244 or vehicle application for 4 weeks.
- Randomization will be 1:1:1 so that an equal number of patients will be treated in each Arm of the study.
- All B244 randomized subjects will be treated at the dose of $1x10^{10}$ cells/ml (O.D. 5.0) or $4x10^{10}$ cells/ml (O.D. 20.0).
- Subjects must be willing and able to complete diary within a consistent time frame on a daily basis and to comply with restrictions on allowable therapies for the duration of the study.
- All subjects will attend a screening visit not more than 21 days prior to Baseline (Day 0). Subjects will be required to return to the clinic at Baseline, Day 14 (Week 2) and Day 28 (Week 4) visits. All subjects will be asked to attend a Week 8 follow-up visit 4 weeks (28 (±3) days) after the last dose of study medication.
- Subjects will apply a total of 10 pumps of IP per application across all affected areas twice-a-day (i.e. 10 pumps in the morning and 10 pumps again at night) for 4 weeks.
- Safety evaluations will consist of review of participant's medical history at screening and on-going assessment of adverse events reported throughout the study duration.

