10.6.4 Day 5- Phone call to patient

The Day 5 visit is a telephone visit that occurs 5 days (±2 days) after the Baseline visit. Study staff will discuss IP application with the subject, answer any questions and counsel the subject on any other matters related to the study.

- phone call to subjects
- application of study drug
- study counseling

10.6.5 Day 14 and Day 28 study visits – Visit 3 and Visit 4

- concomitant medications
- vital signs
- blood for clinical chemistry and hematology (Day 28)
- urine pregnancy test (for women of childbearing potential) (Day 28)
- NRS assessment
- POEM questionnaire
- Pruritus 5-D questionnaire
- IGA scoring assessment
- EASI scoring assessment
- obtain study medication weight for Investigational Product compliance
- dispense investigational product to patient (Day 14)
- collect study medication
- application of study drug
- eDiary
- study counseling
- recording of AEs if any

10.6.6 Day 56-End of Study Visit – Visit 5

- concomitant medications
- vital signs
- physical exam
- urine pregnancy test (for women of childbearing potential)
- NRS assessment
- POEM questionnaire
- Pruritus 5-D questionnaire
- IGA scoring assessment
- EASI scoring assessment
- eDiary
- recording of AEs if any

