2.2 Schedule of Activities

| Visit Name# | Screening | Washout | Baseline | Day 5 | Day 14 | Day 28 | Day 56 | Early |
|------------------------------------|------------|-----------|----------|-------|----------|---------------------------------------|----------|------------|
| | L C | phase | Day 0 | 2 | (Week 2) | (Week 4) | (Week 8) | Terminatio |
| | | 1 | 2 | | , , | , , , , , , , , , , , , , , , , , , , | × , | n Visit |
| Visit Number | V1 | | V2 | | V3 | V4 | V5 | |
| Visit Window in days | -21 to -14 | -14 to -1 | 0 | +/-2 | +/-2 | +/-2 | +/-3 | |
| Informed Consent | Х | | | | | | | |
| Inclusion / Exclusion Criteria | X | | Х | | | | | |
| Demographics | Х | | | | | | | |
| Medical History | Х | | Х | | | | | |
| Concomitant Medications | Х | | Х | | X | Х | Х | X |
| Physical Exam | X | | | | | | X | X |
| Vital Signs | X | | Х | | X | Х | Х | X |
| eDiary | X | Х | Х | Х | X | Х | Х | X |
| POEM | X | | Х | | X | Х | Х | X |
| 5-D Pruritus Scale | X | | Х | | X | Х | Х | X |
| IGA | Х | | Х | | X | Х | Х | X |
| EASI | Х | | Х | | X | Х | Х | X |
| Itch Numeric Rating Scale (NRS) | X | Х | Х | Х | X | Х | Х | X |
| Clinical Labs | X | | | | | Х | | X* |
| Urine pregnancy test for WOCBP | X | | Х | | | Х | X | Х |
| IWRS | | | Х | | | | | |
| Investigational Product compliance | | | Х | | X | Х | | X |
| Dispense study drug | | | Х | | X | | | |
| Application of study drug | | | Х | Х | X | Х | | |
| Phone call to subjects | | Х | | Х | | | | |
| Collect study drug | | | | | X | Х | | X |
| Study counseling | Х | Х | Х | Х | Х | Х | | |

CLINICAL RESEARCH OPTIMIZED™

Protocol: PRB244-01 Confidential STATISTICAL ANALYSIS PLAN

Version 3.0 12-Jan-22

| Visit Name# | Screening | Washout | Baseline | Day 5 | Day 14 | Day 28 | Day 56 | Early |
|----------------------|------------|-----------|----------|-------|----------|----------|----------|------------|
| | | phase | Day 0 | | (Week 2) | (Week 4) | (Week 8) | Terminatio |
| | | | | | | | | n Visit |
| Visit Number | V1 | | V2 | | V3 | V4 | V5 | |
| Visit Window in days | -21 to -14 | -14 to -1 | 0 | +/-2 | +/-2 | +/-2 | +/-3 | |
| AE monitoring | X | | X | | X | X | X | X |

#: Comments/clarification to visits in table below.

*: if visit occurs before Day 28

.....

| Protocol: PRB244-01 | STATISTICAL ANALYSIS PLAN |
|---------------------|---------------------------|
| Confidential | |

Version 3.0 12-Jan-22

| Visit Name | Comments/Clarification |
|---------------------------------|--|

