4 STUDY DESIGN

4.1 General Study Design and Plan

This is a prospective, vehicle-controlled, double-blind, multicenter, randomized phase II trial, comparing the effect of twice daily B244 applications for 4 weeks vs vehicle applications on treatment of mild to moderate pruritus associated with atopic dermatitis.

Approximately 576 subjects are planned to be enrolled.

The total duration of the study will be approximately 11 weeks. Participants will report for a Screening visit and if all inclusion/exclusion criteria are met, subjects will go through a two-week washout phase before reporting for a Baseline visit.

After Screening and Baseline, participants will be randomized to one of two doses of B244 or vehicle application for 4 weeks.

Randomization will be 1:1:1 so that an equal number of patients will be treated in each arm of the study.

STATISTICAL ANALYSIS PLAN

Version 3.0 12-Jan-22

All B244 randomized subjects will be treated at the dose of 1×10^{10} cells/ml (O.D. 5.0) or 4×10^{10} cells/ml (O.D. 20.0).

Subjects must be willing and able to complete diary within a consistent time frame on a daily basis and to comply with restrictions on allowable therapies for the duration of the study.

All subjects will attend a Screening visit not more than 21 days prior to Baseline (Day 0).

Subjects will be required to return to the clinic at Baseline, Day 14 (Week 2) and Day 28 (Week 4) visits. All subjects will be asked to attend a Week 8 follow-up visit 4 weeks (28 (± 3) days) after the last dose of study medication.

Subjects will apply a total of 10 pumps of IP per application across all affected areas twice-a-day (i.e., 10 pumps in the morning and 10 pumps again at night) for 4 weeks.

Safety evaluations will consist of review of participant's medical history at screening and ongoing assessment of adverse events reported throughout the study duration.

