6.5.3 Weekly Average WI-NRS and AI-NRS

For WI-NRS and AI-NRS the weekly average is calculated from the daily scores. For the primary analysis the weekly average will be calculated when there is at least one recorded daily score in the corresponding week. Values from study day (as defined above) Day 1 to 7 contributes to Week 1 average, Study Day 8 to 14 to Week 2, etc. Baseline is derived as the average of the daily scores for Day -7 to -1. The average will be derived as the mean of all non-missing values during the respective time period.

Week 1 WI-NRS = (Sum of daily WI-NRS scores from Day 1 to Day 7) / (Total number of WI-NRS diaries entered from Day 1 to Day 7)

Week 2 WI-NRS = (Sum of daily WI-NRS scores from Day 8 to Day 14) / (Total number of WI-NRS diaries entered from Day 8 to Day 14)

Week 3 WI-NRS = (Sum of daily WI-NRS scores from Day 15 to Day 21) / (Total number of WI-NRS diaries entered from Day 15 to Day 21)

Week 4 WI-NRS = (Sum of daily WI-NRS scores from Day 22 to Day 28 or Day of Visit 4 - 1, whichever is earlier) / (Total number of WI-NRS diaries entered from Day 22 to Day 28 or Day of Visit 4 - 1, whichever is earlier)

Week 5 WI-NRS = (Sum of daily WI-NRS scores from Day of Visit 4 to Day of Visit 4 + 6) / (Total number of WI-NRS diaries entered from Day of Visit 4 to Day of Visit 4 + 6)

Week 6 WI-NRS = (Sum of daily WI-NRS scores from Day of Visit 4 + 7 to Day of Visit 4 + 13) / (Total number of WI-NRS diaries entered from Day of Visit 4 + 7 to Day of Visit 4 + 13)

Week 7 WI-NRS = (Sum of daily WI-NRS scores from Day of Visit 4 + 14 to Day of Visit 4 + 20) / (Total number of WI-NRS diaries entered from Day of Visit 4 + 14 to Day of Visit 4 + 20)

Week 8 WI-NRS = (Sum of daily WI-NRS scores from Day of Visit 4 + 21 to Day of Visit 4 + 27 or Day of Visit 5 - 1, whichever is earlier) / (Total number of WI-NRS diaries entered from Day of Visit 4 + 21 to Day of Visit 4 + 27 or Day of Visit 5 - 1, whichever is earlier)

The same conventions are used to calculate Week 1 to Week 8 AI-NRS.

STATISTICAL ANALYSIS PLAN

Version 3.0 12-Jan-22

Week 1 AI-NRS = (Sum of daily AI-NRS scores from Day 1 to Day 7) / (Total number of AI-NRS diaries entered from Day 1 to Day 7)

Week 2 AI-NRS = (Sum of daily AI-NRS scores from Day 8 to Day 14) / (Total number of AI-NRS diaries entered from Day 8 to Day 14)

Week 3 AI-NRS = (Sum of daily AI-NRS scores from Day 15 to Day 21) / (Total number of AI-NRS diaries entered from Day 15 to Day 21)

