Week 4 AI-NRS = (Sum of daily AI-NRS scores from Day 22 to Day 28 or Day of Visit 4 - 1, whichever is earlier) / (Total number of AI-NRS diaries entered from Day 22 to Day 28 or Day of Visit 4 - 1, whichever is earlier)

Week 5 AI-NRS = (Sum of daily AI-NRS scores from Day of Visit 4 to Day of Visit 4 + 6) / (Total number of AI-NRS diaries entered from Day of Visit 4 to Day of Visit 4 + 6)

Week 6 AI-NRS = (Sum of daily AI-NRS scores from Day of Visit 4 + 7 to Day of Visit 4 + 13) / (Total number of AI-NRS diaries entered from Day of Visit 4 + 7 to Day of Visit 4 + 13)

Week 7 AI-NRS = (Sum of daily AI-NRS scores from Day of Visit 4 + 14 to Day of Visit 4 + 20) / (Total number of AI-NRS diaries entered from Day of Visit 4 + 14 to Day of Visit 4 + 20)

Week 8 AI-NRS = (Sum of daily AI-NRS scores from Day of Visit 4 + 21 to Day of Visit 4 + 27 or Day of Visit 5 - 1, whichever is earlier) / (Total number of AI-NRS diaries entered from Day of Visit 4 + 21 to Day of Visit 4 + 27 or Day of Visit 5 - 1, whichever is earlier)

Sensitivity analysis will be performed on a restricted weekly average, requiring at least 4 responses in the 7 days for each respective time period. Subjects with fewer than 4 responses during the 7-day time period(s) will have their weekly average set to missing.

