6.5.8 Safety Parameters

Safety and tolerability endpoints will consist of all adverse events (AEs) reported during the study duration from the date of randomization through Week 8 (End of Study Visit). Specific AEs are defined below.

STATISTICAL ANALYSIS PLAN

Version 3.0 12-Jan-22

Treatment-Emergent Adverse Events (TEAE): Any AE with onset after the first dose of study medication through 28 days after the last dose of study medication.

Serious Adverse Event (SAE): An AE occurring at any dose that results in any of the following outcomes: death, a life-threatening AE, in-patient hospitalization or prolongation of existing hospitalization, a persistent or significant disability/incapacity, or a congenital anomaly/birth defect.

Associated with Use of the Study Drug: There is a reasonable possibility that the experience may have been caused by the study drug. If the Investigator does not know whether or not study drug caused the event, then the event will be handled as "related to study drug" for reporting purposes. The determination of whether an AE is related to study drug is as follows:

- Related: The AE has a missing, unknown, possible, probable or definite relationship to the study medication.
- Not related: The AE is unlikely or definitely unrelated to the study drug.

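### Visit 5 has two anchors that can disagree, and the Week 8 diary interval can be too short for the fixed four-entry sensitivity rule whichever anchor is kept

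*SAP*

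**What the plan says.** **Timing of Visit 5.** The schedule in SAP 2.2, with the same row in Protocol Appendix A, sets Baseline at Day 0, Visit 4 at Day 28 and Visit 5 at Day 56, with these windows: "Visit Window in days | -21 to -14 | -14 to -1 | 0 | +/-2 | +/-2 | +/-2 | +/-3". Protocol 10.6.6 uses the same label: "10.6.6 Day 56-End of Study Visit – Visit 5". That schedule days count from Baseline is shown by the Day 5 call, which Protocol 10.6.4 places "5 days (±2 days) after the Baseline visit".

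Protocol Section 5 uses a different reference point: "Week 8 follow-up visit 4 weeks (28 (±3) days) after the last dose of study medication". SAP 4.1 repeats it ("Week 8 follow-up visit 4 weeks (28 (± 3) days) after the last dose of study medication"), and the protocol synopsis says the same. No section states which governs.

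**Last dose of a completer.** Protocol 8.6 has the subject use the last bottle up to the Week 4 visit, and both schedules mark an application at that visit. SAP 6.5.6 ends the treatment period on the day before Visit 4, while recognising that a subject may have applied product on the visit day. The last dose can therefore be on the Visit 4 day or the day before.

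**Week 8 diary week.** SAP 6.5.3 takes the Week 8 average over the days "from Day of Visit 4 + 21 to Day of Visit 4 + 27 or Day of Visit 5 - 1, whichever is earlier". The main analysis needs one entry. The sensitivity analysis needs four: "Subjects with fewer than 4 responses during the 7-day time period(s) will have their weekly average set to missing".

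**The concern.** There are two problems. They share the Visit 5 date but have different causes.

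First, the two anchors coincide only when a completer's last dose falls on Day 28. Visit 4 has its own tolerance of two days, so a Visit 5 date can be in window under one statement and out under the other. Window compliance then depends on which section is read.

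Second, the Week 8 interval is bounded by two movable visits. When Visit 4 is late and Visit 5 early, the interval shrinks, but the sensitivity minimum stays at four entries. A subject who filled in the diary every day can then be set to missing because of visit timing alone. A rule meant to screen out sparse diaries should not do that. The rule feeds the Week 8 rows of the WI-NRS and AI-NRS sensitivity tables.

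**Working it through.** **Inputs.** Visit 4 on Day 26–30 and Visit 5 on Day 53–59 (SAP 2.2, Protocol Appendix A). Last-dose window: last dose + 25 to + 31 (Protocol Section 5, SAP 4.1). Week 8 bounds and the four-entry minimum (SAP 6.5.3). Only the gap V5 − V4 matters, so the SAP's renumbering of Day 0 as Day 1 changes nothing.

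**Nominal case.** Last dose on Day 28 gives 28 + 28 = Day 56, so the documents agree at the centre.

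**All schedule-valid pairs.** There are 5 × 7 = 35. Week 8 diary days = min(V4 + 27, V5 − 1) − (V4 + 21) + 1 = min(7, gap − 21).

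| Gap V5 − V4 (days) | Pairs | Week 8 diary days |
|---|---|---|
| 23 | 1 | 2 |
| 24 | 2 | 3 |
| 25 | 3 | 4 |
| 26 | 4 | 5 |
| 27 | 5 | 6 |
| 28 | 5 | 7 |
| 29 | 5 | 7 |
| 30 | 4 | 7 |
| 31 | 3 | 7 |
| 32 | 2 | 7 |
| 33 | 1 | 7 |

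**Disagreement between anchors.**
- Last dose on the Visit 4 day: the last-dose window needs a gap of 25–31. Gaps 23, 24, 32 and 33 fail: 1 + 2 + 2 + 1 = 6 of 35 (17%). The pairs (V4, V5) are (26,58), (26,59), (27,59), (29,53), (30,53) and (30,54). Another 6 pairs satisfy the last-dose rule but lie outside the schedule: (26,51), (26,52), (27,52), (29,60), (30,60) and (30,61).
- Last dose on the day before Visit 4: the window needs a gap of 24–30. Gaps 23, 31, 32 and 33 fail: 1 + 3 + 2 + 1 = 7 of 35 (20%), with 7 pairs in the reverse direction.

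**Short Week 8 under the schedule.** Fewer than four days occurs at gaps 23 and 24: (30,53) with 2 days, and (29,53) and (30,54) with 3. That is 3 of 35.

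**Short Week 8 under the last-dose rule.**
- Last dose on the Visit 4 day: smallest gap 25, so at least 4 days.
- Last dose on the day before: smallest gap 24, so 3 days.
- Last dose fixed at Day 27 (28 consecutive days from Day 0, as in Protocol 8.7): the window is Day 52–58. Visit 4 on Day 30 with Visit 5 on Day 53 is then in window under both anchors with 2 diary days, and Visit 5 on Day 52 leaves 1.

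The last-dose anchor therefore does not by itself guarantee four days.

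**Share of subjects (assumptions, since the documents give no distribution of visit days).**
- All pairs equally likely: 3/35 = 8.6%.
- Visits clustered near nominal, with triangular weights 1-2-3-2-1 for Visit 4 and 1-2-3-4-3-2-1 for Visit 5: the total weight is 9 × 16 = 144. The affected pairs contribute 1×1 + 2×1 + 1×2 = 5, giving 5/144 = 3.5%.

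**Check on Week 4.** The earliest in-window Visit 4 is protocol Day 26, which is SAP Day 27. Week 4 then covers SAP Days 22–26, five days, so four entries are always attainable for an in-window visit.

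**The case against.** The best reply on the anchors is that they can be read together. The schedule prints a nominal label and a bare ±3, while the text sections give the same ±3 and say what it is measured from, so the schedule could be shorthand. That reading is possible, but no section states it. Protocol 10.6.4 shows schedule days counted from Baseline, and the two readings give different answers in 6 or 7 of 35 pairs. The need to reconcile stands.

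The best reply on the diary rule is that little depends on it. The named primary, secondary and exploratory endpoints are at Week 4 or Week 2. Week 8 is reported because all weeks are, and SAP 7.4 treats p-values beyond the primary endpoint as exploratory. The main Week 8 average needs one entry, and a subject's other weeks stay in the repeated-measures model. This stands and limits the weight of the point.

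A reader might infer more than the documents support in four ways:

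- *That choosing the last-dose anchor cures the short Week 8.* It does so only if the last dose is on the Visit 4 day.
- *That sites cannot tell which visits are deviations.* SAP 7.3.2 refers classification to a separate deviation guidance that is not among these documents. SAP 6.5.10 also keeps site-visit data under the recorded visit even when out of window.
- *That the anchor conflict leaves adverse events unobserved.* SAP 6.5.8 counts treatment-emergent events as "Any AE with onset after the first dose of study medication through 28 days after the last dose of study medication". With a last dose on the Visit 4 day, a 23-day gap stops 5 days short. But the ±3 tolerance in the last-dose rule already allows 3 days short, so the schedule adds at most 2 in that case.
- *That 9% of completers will be lost.* That figure needs uniform, independent visit days; clustering lowers it.

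**Conclusion.** The point holds as two limited defects. The documents give Visit 5 two anchors without a precedence rule, and these disagree for 6 of 35 schedule-valid pairs (7 of 35 if the last dose is on the day before Visit 4). Independently, SAP 6.5.3 can make the four-entry sensitivity minimum unattainable at Week 8: as few as 2 days under the schedule, and 3 under the last-dose rule when the last dose is on the day before Visit 4. Three of 35 schedule-valid pairs are affected.

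The pair counts follow from the stated windows for completers. The conversion to roughly 9% or 3.5% of subjects rests on assumed visit timing. The loss is confined to Week 8 WI-NRS and AI-NRS results in sensitivity analyses. The Week 4 primary endpoint and the main Week 8 analysis are not affected by the four-entry rule. This is worth correcting because it is cheap, not because it threatens a main conclusion.

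**What to change.** 1. Reconcile the Visit 5 rows in Protocol Appendix A and SAP 2.2 (and the label in Protocol 10.6.6) with the protocol synopsis, Protocol Section 5 and SAP 4.1, so that one anchor applies throughout. Which anchor is for the sponsor to decide.

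2. Whichever is chosen, state the Week 8 sensitivity minimum in SAP 6.5.3 as at least 4/7 of the days available in the interval, rounded up. This gives 4 entries for 7 or 6 days, 3 for 5 or 4 days, and 2 for 3 or 2 days. A complete diary is then never set to missing, and a full week is treated as now. SAP 7.5.4 already scales rescue medication days to the actual interval length, so the principle is not new to the plan.

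**Cost.** Wording only, with no added visits or assessments. The small downside is that a few averages based on 2 or 3 days enter an analysis intended to exclude sparse weeks. The number of days available should be shown beside those results.

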2.3 Schedule of eDiary and Efficacy Assessments

eDiary (ePRO) is provided to subjects at the screening visit for daily entry at home (e.g., application on smartphone). Questionnaires and clinician assessments are recorded via ePRO/eCOA (e.g., tablet) or CRF during the site visits per schedule of events. Additional patient reported information include rescue medication use, dose administration confirmation, and adjunctive therapy use.

| Device | Assessment | Frequency and Duration of Assessment |
|----------|--|--|
| eDiary | WI-NRS | Once daily from Screening visit through the Follow-up visit |
| eDiary | AI-NRS | Once daily from Screening visit through the Follow-up visit |
| eDiary | Patient Reported Local Tolerability | Once daily from Day 1 to Day 7 of treatment |
| eDiary | POEM | Patient reported at site visits |
| eDiary | 5-D Pruritus Scale | Patient reported at site visits |
| eCOA/CRF | IGA | Clinician assessment at site visits |
| eCOA/CRF | EASI | Clinician assessment at site visits |

STATISTICAL ANALYSIS PLAN

Version 3.0 12-Jan-22

3 STUDY OBJECTIVE AND ENDPOINTS

3.1 Study Objectives

3.1.1 Primary Objective

To assess the efficacy of B244 in the treatment of pruritus in adults with a history of atopic dermatitis.

3.1.2 Secondary Objectives

To assess the safety and tolerability of B244 in adults with a history of atopic dermatitis.

3.2 Study Endpoints

3.2.1 Efficacy - Primary Endpoint

The primary efficacy endpoint is:

• Mean change (absolute) in WI-NRS from Baseline to Week 4

3.2.2 Efficacy - Secondary Endpoints

The secondary efficacy endpoints are:

- Proportion of subjects with \geq 4point improvement in WI-NRS from Baseline to Week 4
- Proportion of subjects with any improvement in WI-NRS from Baseline to Week 4
- Mean change (absolute and percent) in AI-NRS from Baseline to Week 4
- Proportion of subjects with \geq 4 point improvement in AI-NRS from Baseline to Week 4
- Proportion of subjects with any improvement in AI-NRS from Baseline to Week 4
- Mean change (absolute and percent) in WI-NRS from Baseline to Week 2
- Proportion of subjects with \geq 4 point improvement in WI-NRS from Baseline to Week 2
- Mean change (absolute and percent) in POEM from Baseline to Week 4
- Mean change (absolute and percent) in 5-D Pruritus Scale from Baseline to Week 4

The endpoints will be reported for all weeks or all visits. The primary endpoint of mean change in WI-NRS is also presented at all weeks for both absolute and percent change. Absolute change will be considered the primary endpoint with percent change as supportive. Any improvement in WI-NRS and AI-NRS is defined as ≥ 1 point improvement from Baseline.

